Appendix C: Informed Consent (Template)

Appendix D: Case Report Forms (CRFs)

Protocol Synopsis**Protocol ID 4600**

Sponsor	Torax Medical, Inc. [name] [contact] [contact]
Study Title	RELIEF Study: A Prospective, Multicenter Study of Reflux Management with the LINX® System for Gastroesophageal Reflux Disease after Laparoscopic Sleeve Gastrectomy
Study Device	The LINX® Reflux Management System (LINX)
Indication	The LINX® Reflux Management System is a laparoscopic, fundic-sparing anti-reflux procedure indicated for patients diagnosed with Gastroesophageal Reflux Disease (GERD) as defined by abnormal pH testing, and who are seeking an alternative to continuous acid suppression therapy (i.e. proton pump inhibitors or equivalent) in the management of their GERD.
FDA Approval	March 22, 2012
Study Design	An observational, multicenter, single-arm study with prospective enrollment.
Purpose	To evaluate the safety and efficacy of LINX for its approved indication in patients who have had prior gastric surgery, specifically, laparoscopic sleeve gastrectomy (LSG).
Objective	To confirm safety and efficacy after LSG in patients indicated for LINX is similar to the outcomes that formed the basis for Premarket Approval (PMA) to support modification of the current labeling with a statement that prior gastric surgery with LSG has been evaluated for safety and efficacy.
Number of Subjects	Up to 30 subjects
Study Centers	Up to 12 implanting sites in the U.S.
Study Duration	36 months (24-month enrollment period + 12-month follow-up period)
Evaluation of Safety	Rate of serious device and procedure related adverse events assessed by reporting all adverse events and by estimating the rate of serious device and procedure related adverse events through 12 months post implantation. Safety will also be evaluated by endoscopy to assess the mucosa and abdominal/chest X-ray evaluations to verify device location at 12 months post implantation.
Evaluation of Efficacy	Percentage of subjects reporting at the 12-month follow-up: 
• Normalization of total distal acid exposure (% total time pH<4) or at least 50% reduction in total distal acid exposure compared to baseline• At least 50% reduction in total GERD-HRQL score compared to baseline (off PPIs)• At least 50% reduction in average daily PPI dosage compared to baseline
Study Management	Torax Medical Inc. or Designate

Schedule of Data Collection

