6.0 SELECTION AND WITHDRAWAL OF SUBJECTS

6.1 INCLUSION CRITERIA

Subjects included in the study must meet all the following criteria:

1. Age >22 years
2. Laparoscopic sleeve gastrectomy (LSG) for obesity ≥ 12 months prior to proposed device implantation date.
3. Subject is a surgical candidate, i.e. is able to undergo general anesthesia and laparoscopic surgery.
4. Documented typical symptoms of GERD for longer than 6 months (regurgitation or heartburn which is defined as a burning epigastric or substernal pain which responds to acid neutralization or suppression).
5. Subject requires daily proton pump inhibitor or other anti-reflux drug therapy.

6. Total distal ambulatory esophageal pH must meet the following criteria: pH <4 for $\geq 4.5\%$ of the time. Note: Subjects shall have discontinued any GERD medications for at least 7 days prior to testing, with the exception of antacids up to the morning of testing.
7. Subjects with symptomatic improvement on PPI therapy demonstrated by a GERD-HRQL score of ≤ 10 **on** PPI and ≥ 15 **off** PPI, or subjects with a >6 point improvement when comparing their **on** PPI and **off** PPI GERD-HRQL scores.
8. GERD symptoms, in absence of PPI therapy (minimum 7 days).
9. If the subject is of child bearing potential must have a negative pregnancy test within one week prior to implant and must agree to use effective means of birth control during the course of the study.
10. Subject is willing and able to cooperate with follow-up examinations
11. Subject has been informed of the study procedures and the treatment and has signed an informed consent form.

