8.5.1 Esophageal Acid Exposure

Testing will be performed with subjects off PPIs. The subject's total distal esophageal acid exposure time at baseline will serve as the control and will be compared to results at the 12-month visit. Normalization for total distal ambulatory esophageal pH testing is defined as pH < 4 for < 4.5% of the time. If longer pH evaluations are received, the total distal acid exposure time will be recorded as a 24-hour average (e.g. 48-hour Bravo testing).

The proportion of subjects achieving pH normalization or at least a >50% reduction from baseline to the result at the 12-months will be summarized descriptively for the FAS. Two-sided 95% CI will also be constructed using exact Clopper-Pearson method.

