8.5.2 Quality of Life

Subjects GERD-HRQL (Health Related Quality of Life) scores will be assessed off all GERD medications. The subject's baseline GERD-HRQL score will serve as the control and be compared to the subject's GERD-HRQL 12 months post implantation.

Summary statistics will be provided for the GERD-HRQL questionnaire. Subjects are asked to rate 10 specific symptoms in addition to assessing how satisfied they are with their present condition. Each symptom is scored on a 0 to 5 scale. Summaries will also be provided for an overall score which is calculated as the average of the ten components for each subject.

Counts and percentages will be provided for responses to the GERD-HRQL questionnaire.

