Median (Min, Max)	xx.x (xx, xx)	xx.x (xx, xx)

Denominator and percentages are based on subjects with non-missing data.

Table 6
 Bravo pH Normalization or $\geq 50\%$ Reduction Compared to Baseline (Off PPI)
 Full Analysis Set

Parameter	Baseline	12 Months Follow-Up	Change from Baseline to 12 Months Follow-Up	% Successful at 12 Months Follow-Up [1]
Total % Time				
n	xx	xx	xx	
Mean (SD)	xx.x (xx.x)	xx.x (xx.x)	xx.x (xx.x)	
Median (Min, Max)	xx.x (xx, xx)	xx.x (xx, xx)	xx.x (xx, xx)	
95% Confidence Interval			(xx.xxx, xx.xxx)	
p-value[2]			0.xxx	
Number of Subjects were Successful				xx (xx.x%)
Number of subjects with pH normalization ($\leq 4.5\%$)				xx (xx.x%)
Number of subjects with $\geq 50\%$ reduction in total distal acid exposure				xx (xx.x%)

Denominator and percentages are based on subjects completed baseline and 12 months follow-up.

[1] % Successful is defined as number of subjects meeting the success criterion of pH normalization or at least 50% reduction in total distal acid exposure.

[2] From one-sample, paired t test against the change from baseline is equal to zero.

Table 7
Summary of DeMeester Score Components
Full Analysis Set

Parameter	Baseline	12 Months Follow-Up	Change from Baseline to 12 Months Follow-Up
Daily Average of Total % Time			
n	xx	xx	xx
Mean (SD)	xx.x (xx.x)	xx.x (xx.x)	xx.x (xx.x)
Median (Min, Max)	xx.x (xx, xx)	xx.x (xx, xx)	xx.x (xx, xx)
Daily Average of Upright % Time			
n	xx	xx	xx
Mean (SD)	xx.x (xx.x)	xx.x (xx.x)	xx.x (xx.x)
Median (Min, Max)	xx.x (xx, xx)	xx.x (xx, xx)	xx.x (xx, xx)
Daily Average of Supine % Time			
n	xx	xx	xx
Mean (SD)	xx.x (xx.x)	xx.x (xx.x)	xx.x (xx.x)
Median (Min, Max)	xx.x (xx, xx)	xx.x (xx, xx)	xx.x (xx, xx)
Daily Average of Number of Reflux Episodes (pH <4)			
n	xx	xx	xx
Mean (SD)	xx.x (xx.x)	xx.x (xx.x)	xx.x (xx.x)
Median (Min, Max)	xx.x (xx, xx)	xx.x (xx, xx)	xx.x (xx, xx)
Daily Average of Number of Reflux Episodes > 5 mins			
n	xx	xx	xx
Mean (SD)	xx.x (xx.x)	xx.x (xx.x)	xx.x (xx.x)
Median (Min, Max)	xx.x (xx, xx)	xx.x (xx, xx)	xx.x (xx, xx)
Daily Average of Longest Reflux Episode (min)			
n	xx	xx	xx
Mean (SD)	xx.x (xx.x)	xx.x (xx.x)	xx.x (xx.x)
Median (Min, Max)	xx.x (xx, xx)	xx.x (xx, xx)	xx.x (xx, xx)

Note: For all parameters, the within subject average of the values within a visit is first calculated prior to summarizing across all subjects at the given visit.

Table 7
 Summary of DeMeester Score Components
 Full Analysis Set

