5 - Symptoms are incapacitating, unable to do activities	xx (xx.x%)	xx (xx.x%)	xx (xx.x%)	xx (xx.x%)

Denominator and percentages are based on subjects completed questionnaires per protocol requirements.

Table 13
 Summary of GERD-HRQL Questionnaire (Off PPI)
 Full Analysis Set

Characteristic	Baseline	3 Months Follow-Up	6 Months Follow-Up	12 Months Follow-Up
Do you have bloating or gassy feelings?				
0 - No symptoms	xx (xx.x%)	xx (xx.x%)	xx (xx.x%)	xx (xx.x%)
1 - Symptoms noticeable, but not bothersome	xx (xx.x%)	xx (xx.x%)	xx (xx.x%)	xx (xx.x%)
2 - Symptoms noticeable and bothersome, but not every day	xx (xx.x%)	xx (xx.x%)	xx (xx.x%)	xx (xx.x%)
3 - Symptoms bothersome every day	xx (xx.x%)	xx (xx.x%)	xx (xx.x%)	xx (xx.x%)
4 - symptoms affect daily activities	xx (xx.x%)	xx (xx.x%)	xx (xx.x%)	xx (xx.x%)
5 - Symptoms are incapacitating, unable to do activities	xx (xx.x%)	xx (xx.x%)	xx (xx.x%)	xx (xx.x%)
If you take medication, does this affect your daily life?				
0 - No symptoms	xx (xx.x%)	xx (xx.x%)	xx (xx.x%)	xx (xx.x%)
1 - Symptoms noticeable, but not bothersome	xx (xx.x%)	xx (xx.x%)	xx (xx.x%)	xx (xx.x%)
2 - Symptoms noticeable and bothersome, but not every day	xx (xx.x%)	xx (xx.x%)	xx (xx.x%)	xx (xx.x%)
3 - Symptoms bothersome every day	xx (xx.x%)	xx (xx.x%)	xx (xx.x%)	xx (xx.x%)
4 - symptoms affect daily activities	xx (xx.x%)	xx (xx.x%)	xx (xx.x%)	xx (xx.x%)
5 - Symptoms are incapacitating, unable to do activities	xx (xx.x%)	xx (xx.x%)	xx (xx.x%)	xx (xx.x%)
How satisfied are you with your present condition?				
Satisfied	xx (xx.x%)	xx (xx.x%)	xx (xx.x%)	xx (xx.x%)
Neutral	xx (xx.x%)	xx (xx.x%)	xx (xx.x%)	xx (xx.x%)
Dissatisfied	xx (xx.x%)	xx (xx.x%)	xx (xx.x%)	xx (xx.x%)
GERD-HRQL Total Score				
n	xx (xx.x%)	xx (xx.x%)	xx (xx.x%)	xx (xx.x%)
Mean (SD)	xx (xx.x%)	xx (xx.x%)	xx (xx.x%)	xx.x (xx.xx)
Median(Min, Max)	xx (xx.x%)	xx (xx.x%)	xx (xx.x%)	xx.x (xx, xx)
95% Confidence Interval	(xx.XXX, xx.XXX)	(xx.XXX, xx.XXX)	(xx.XXX, xx.XXX)	(xx.XXX, xx.XXX)

Denominator and percentages are based on subjects completed questionnaires per protocol requirements.

Table 14
GERD-HRQL Total Score (Off PPI)
Full Analysis Set

Parameter	Baseline	12 Months Follow-Up	Change from Baseline to 12 Months Follow-Up	% Successful at 12 Months Follow-Up [1]
GERD-HRQL Total Score				
n	xx	xx	xx	
Mean (SD)	xx.x (xx.x)	xx.x (xx.x)	xx.x (xx.x)	
Median (Min, Max)	xx.x (xx, xx)	xx.x (xx, xx)	xx.x (xx, xx)	
95% Confidence Interval			(xx.xxx, xx.xxx)	

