Yes	xx (xx.x%)	xx (xx.x%)	xx (xx.x%)	xx (xx.x%)
No	xx (xx.x%)	xx (xx.x%)	xx (xx.x%)	xx (xx.x%)
No need to vomit	xx (xx.x%)	xx (xx.x%)	xx (xx.x%)	xx (xx.x%)
Ability to belch				
Yes	xx (xx.x%)	xx (xx.x%)	xx (xx.x%)	xx (xx.x%)
No	xx (xx.x%)	xx (xx.x%)	xx (xx.x%)	xx (xx.x%)

Denominator and percentages are based on subjects with non-missing data.

Table 18
 Regurgitation Severity Elimination from Severe and Moderate (Off PPI)
 Full Analysis Set

Change from Baseline	3 Months Follow-Up (N = ##)	6 Months Follow-Up (N = ##)	12 Months Follow-Up (N = ##)
Eliminate severe (to moderate, mild or none) [1]	xx (xx.x%)	xx (xx.x%)	xx (xx.x%)
Eliminate moderate (to mild or none) [2]	xx (xx.x%)	xx (xx.x%)	xx (xx.x%)

Column header counts represent the number of subjects who complete the FSQ form at the given visit.

[1] Percentages are calculated using the number of subjects with severe regurgitation at baseline and who complete the FSQ form at the given visit.

[2] Percentages are calculated using the number of subjects with moderate regurgitation at baseline and who complete the FSQ form at the given visit.

Table 19
 Regurgitation Frequency Summary (Off PPI)
 Full Analysis Set

Frequency	Baseline (N = ##)	3 Months Follow-Up (N = ##)	6 Months Follow-Up (N = ##)	12 Months Follow-Up (N = ##)
Regurgitation (times/week)				
n	xx	xx	xx	xx
Mean (SD)	xx.x (xx.x)	xx.x (xx.x)	xx.x (xx.x)	xx.x (xx.x)
Median (Min, Max)	xx.x (xx, xx)	xx.x (xx, xx)	xx.x (xx, xx)	xx.x (xx, xx)

Table 20
Adverse Events Summary
Full Analysis Set

Adverse Event Category	Number of Subjects (N = ##)	Number of Events
Any Adverse Events	xx (xx.x%)	xx
Serious Adverse Events	xx (xx.x%)	xx
AE related (Yes/Probably/Possibly or Unknown) to Study Device	xx (xx.x%)	xx
AE related (Yes/Probably/Possibly or Unknown) to Implant Procedure	xx (xx.x%)	xx
SAE related (Yes/Probably/Possibly or Unknown) to Study Device	xx (xx.x%)	xx
SAE related (Yes/Probably/Possibly or Unknown) to Implant Procedure	xx (xx.x%)	xx

All percentages are calculated using the number of subjects in the FAS as the denominator.

Table 21
All Adverse Events
Full Analysis Set

Adverse Event Category	Number of Subjects (N = ##)	Number of Events
Total	xx (xx.x%)	xx
Achalasia	xx (xx.x%)	xx
Allergic reaction	xx (xx.x%)	xx
Anaphylaxis	xx (xx.x%)	xx
....	xx (xx.x%)	xx

All percentages are calculated using the number of subjects in the FAS as the denominator.

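### SAP Table 6 counts acid exposure of exactly 4.5% as normal, against the plan's own <4.5% definition; the regurgitation rows and the GERD-HRQL score wording need smaller repairs

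*SAP*

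**What the plan says.** **pH normalization.** SAP 8.5.1 states: "Normalization for total distal ambulatory esophageal pH testing is defined as pH < 4 for < 4.5% of the time". Protocol 10.1.1 gives the same definition. Inclusion criterion 6 in protocol 6.1 is its complement: "Total distal ambulatory esophageal pH must meet the following criteria: pH <4 for $\geq 4.5\%$ of the time". The row label in SAP Table 6 reads "Number of subjects with pH normalization ($\leq 4.5"%). Table 6 footnote [1] defines success as normalization or a fall of 50% or more, and gives no numerical limit for normalization.

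**Regurgitation.** Protocol 10.3 and SAP 8.7 list, among the additional analyses at 3, 6 and 12 months, the percentage of subjects who eliminate moderate or severe regurgitation on the Foregut Symptoms Questionnaire (FSQ). Table 18 has two rows with separate denominators. The first is "Eliminate severe (to moderate, mild or none) [1"], over subjects severe at baseline. The second counts moderate to mild or none, over subjects moderate at baseline.

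**GERD-HRQL.** The Protocol Synopsis sets the endpoint as "At least 50% reduction in total GERD-HRQL score compared to baseline (off PPIs"). Table 14 is titled "GERD-HRQL Total Score (Off PPI"), and Tables 12 and 13 also report a total score. SAP 8.5.2 describes ten items scored 0 to 5 and adds: "Summaries will also be provided for an overall score which is calculated as the average of the ten components for each subject". Inclusion criterion 7 uses limits of 10 on PPI and 15 off PPI, "or subjects with a >6 point improvement when comparing their" on-PPI and off-PPI scores.

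**The concern.** The acid-exposure responder rate is one of three efficacy measures, and the study is meant to support a labeling statement. No hypothesis test rests on it, so the reported percentage and its interval are the result. A responder threshold needs one definition. Here the text and the shell disagree at exactly the value where entry and normalization meet, and the shell's error can only favor the device.

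In Table 18, a subject who goes from severe to moderate still has moderate regurgitation but is counted under elimination. Both rows can then look better than the outcome that the protocol names.

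For GERD-HRQL, the one score whose calculation SAP 8.5.2 spells out lies on a 0–5 scale, while the tables report a total that the visible text never defines.

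**Working it through.** The plan has no figure to reproduce: SAP section 7 says that no formal sample size calculation was made. The check compares the rules and works out their consequences.

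**1. pH cut-off**

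Inputs: baseline B ≥ 4.5% (protocol 6.1); normalization at 12-month value F < 4.5% (protocol 10.1.1, SAP 8.5.1) or F ≤ 4.5% (Table 6); alternative route F ≤ B/2, taking the rule as a reduction of 50% or more, as in protocol 5.2 and Table 6; up to 30 subjects (SAP 7).

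- The two limits differ only at F = 4.5%.
- At F = 4.5% the alternative route already gives success if B/2 ≥ 4.5, that is B ≥ 9.0%.
- Composite success therefore changes only for F = 4.5% with 4.5% ≤ B < 9.0%. In steps of 0.1% that is B = 4.5 to 8.9, or (8.9 − 4.5)/0.1 + 1 = 45 baseline values.
- Enumerating B from 4.5 to 30.0 and F from 0 to 30.0 (256 × 301 = 77,056 pairs) gives 45 disagreements, all of this form.
- The separate normalization row changes at F = 4.5% for any baseline.
- Shift per subject = 100/n: 3.3 points at n = 30, 5.0 at n = 20, 6.7 at n = 15. The last two sizes are assumptions. Table 6 counts only subjects with both visits, and SAP 8.8 reports that early follow-up was lower than expected.
- Assumed example with Clopper-Pearson 95% limits: 21/30 = 70.0% (50.6 to 85.3) becomes 22/30 = 73.3% (54.1 to 87.7).

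**2. Regurgitation**

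Assumed counts: 10 severe, 10 moderate and 10 mild at baseline, all with an FSQ at follow-up. Follow-up is given as severe / moderate / mild.

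- Pattern A: severe 2/4/4, moderate 0/4/6, mild 0/0/10.
- Pattern B: severe 2/3/5, moderate 0/4/6, mild 0/1/9.

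Both patterns have follow-up totals of 2/8/20 in Table 17 and rows of 8/10 = 80% and 6/10 = 60% in Table 18. The share of baseline moderate-or-severe subjects who reach mild or none is:

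- A: (4 + 6)/20 = 50%, below both rows.
- B: (5 + 6)/20 = 55%.

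In general, let a be the number moving from severe to moderate and m the number moving from mild to moderate. With these margins the 2 severe places are filled by subjects who stayed severe, so a + 4 + m = 8 and a = 4 − m. The combined count is (8 − a) + 6 = 14 − a. As a runs from 0 to 4, the count runs from 14 to 10 of 20, or 70% to 50%.

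So Tables 17 and 18 do not fix the combined figure in general. They do if nobody who was mild or none at baseline becomes moderate or severe; worsening from none to mild does no harm.

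**3. GERD-HRQL**

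Ten items scored 0 to 5 give a sum of 0 to 50 and an average of 0 to 5. Entry limits of 10 and 15 and a gain of more than 6 points are impossible on an average, so they imply the sum. On complete forms, with S0 and S12 the baseline and 12-month sums, S12/10 ≤ 0.5 × S0/10 is the same condition as S12 ≤ 0.5 × S0. Over baseline sums 1 to 50 and follow-up sums 0 to 50 (50 × 51 = 2,550 pairs), none changes responder status. Means, changes and interval limits differ tenfold: −20 on the sum is −2.0 on the average.

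**The case against.** **pH.** The two passages that define normalization agree; only a shell label differs, and the SAP appendix calls the shells a guide to layout. Averages over several recording days need not fall on a 0.1% grid, so a value of exactly 4.5% may be rare. This stands as to size. It does not remove the error: SAP 8.1 waives an amendment only for changes that do not touch methodology or conclusions, and a threshold is not layout. A reader might infer that the pH success rate is materially inflated. The documents do not support that, because only one exact value is affected.

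**Regurgitation.** This is an additional analysis, not one of the three efficacy criteria. Table 18 states openly what each row counts, and its two rows can be read as two separate eliminations. The FSQ listing would let someone count the combined outcome by hand. All of this stands and keeps the item secondary. A reader might also infer that the plan omits the combined percentage altogether. That cannot be concluded, since Tables 22 to 28 were not in the text available here.

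**GERD-HRQL.** The word 'also' in SAP 8.5.2 lets the average be an extra summary beside the total, and the entry limits and table titles point to a 0–50 sum. This largely stands. A reader might infer that the average contradicts the endpoint or puts the responder rate in doubt. It does neither on complete forms. What remains is that the visible text never writes out the sum and that no visible shell shows the average.

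**Conclusion.** The main point holds: Table 6 is wrong as written on the normalization limit. The effect is confined to 12-month values of exactly 4.5%. For composite success it is further confined to baselines of 4.5% to below 9.0%, assuming that the 50% route includes exactly 50% and that the programmer applies the row's limit to the composite. One such subject is worth 3.3 points at n = 30.

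The Table 18 point holds as a secondary one. Its rows do not give the outcome named in protocol 10.3 and SAP 8.7, and the 50% to 70% range rests on invented counts that show what is possible, not what happened. It is conditional on the combined figure not being in a table outside the available text.

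The GERD-HRQL point is minor wording. Only the scale of means, changes and confidence limits is at stake.

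**What to change.** 1. In Table 6, change the normalization label from ≤4.5% to <4.5%, and apply that limit to the composite as well. Against the present label this can only keep or lower the reported rate.
2. Unless a combined percentage already appears in Tables 22 to 28, keep the two rows of Table 18 and add a third. Its numerator is subjects moderate or severe at baseline who are mild or none at the visit. Its denominator is all subjects moderate or severe at baseline with an FSQ at that visit. The downside is that this percentage may be lower than the existing rows.
3. In SAP 8.5.2, state that the GERD-HRQL total is the sum of the ten items (0 to 50) and is the score in Tables 12 to 14. Label the average as an additional summary.

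These are edits to SAP text and shells. Total acid-exposure time, the ten items and the regurgitation grade are already collected.

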4.0 STUDY RATIONALE

The LSG procedure involves removal of the fundus. As a result, fundoplication is extremely difficult to perform with the limited amount of fundus tissue present in patients with prior LSG. Roux-en-Y Gastric bypass (RYGB) has been recommended as a conversion procedure for those who develop or continue to have reflux after LSG. However, LINX has been considered as an alternative and less invasive option that may potentially have fewer complications compared to RYGB. Additionally, patients may not be interested in RYGB due its associated malabsorption. The LINX device is implanted in the area of the gastroesophageal junction (GEJ), which is largely undisturbed with LSG. Patients with prior gastric surgery, such as LSG, have not to date been enrolled in clinical studies for the LINX device. This study is the first to prospectively enroll and evaluate under protocol the LINX device for GERD in post-LSG patients.

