6.2 EXCLUSION CRITERIA

Subjects should be excluded from the study based on the following criteria:

1. The procedure is an emergency procedure.
2. Suspected or known allergies to titanium, stainless steel, nickel, or ferrous materials.
3. Presence of >3 cm hiatal hernia as determined by endoscopy or barium esophagram.
4. Subject had any major complications related to the laparoscopic sleeve gastrectomy that may interfere with, or increase the risks of the LINX procedure (such as, but not limited to, leaks from the gastric remnant and infection at the sleeve gastrectomy)
5. Plans to surgically revise the gastric pouch (either known preoperatively or decided intraoperatively)
6. Currently being treated with another investigational drug or investigational device.
7. Suspected or confirmed esophageal or gastric cancer or prior gastric or esophageal surgery or endoscopic intervention for GERD (with the exception of sleeve gastrectomy).
8. Distal amplitude <35 mmHg or <70% peristaltic sequences (if using Conventional Manometry)

-or-

If using High Resolution Manometry (exclude for any of the following):

- Distal Contractile Integral (DCI) ≤ 450 mmHg·s·cm or
- $\geq 50\%$ ineffective swallows or
- $\geq 50\%$ fragmented swallows

(Fragmented swallows are defined as those with a ≥ 5 cm break [large] in peristaltic integrity)

9. Presence of esophagitis – Grade C or D (LA Classification).
10. BMI >35.
11. Symptoms of dysphagia more than once per week within the last 3 months.
12. Diagnosed with Scleroderma.
13. Diagnosed with an esophageal motility disorder such as but not limited to achalasia, nutcracker esophagus, or diffuse esophageal spasm or hypertensive LES.
14. Subject has a history of or known esophageal stricture or gross esophageal anatomic abnormalities (Schatzki's ring, obstructive lesions, etc.)
15. Subject has esophageal or gastric varices
16. History of/or known Barrett's esophagus.
*Note: The diagnosis of Barrett's esophagus requires both **endoscopic** and **histologic** evidence of metaplastic columnar epithelium. Endoscopically, there must be columnar epithelium within the esophagus. Histologically, the epithelium must be metaplastic, as defined by the presence of goblet cells.*
17. Subject cannot understand trial requirements or is unable to comply with follow-up schedule
18. Pregnant or nursing, or plans to become pregnant during the course of the study.

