1.2 Study Design

This is an observational, multicenter, single-arm study with prospective enrollment. Based on the observational status of the study, no formal statistical hypothesis tests will be conducted. Up to 30 subjects meeting the eligibility requirements will be implanted with LINX and followed through 12-months after implant. Up to twelve clinical sites will enroll subjects. Safety evaluations will be ongoing throughout the duration of the study, starting at the implant procedure. Efficacy endpoints will be evaluated at the 12-month visit.

Safety will be assessed by evaluating device and/or procedure related adverse events, perioperative complications, device malfunctions, device removals, and hospital readmissions experienced by subjects post-LINX implant out to 12 months. Esophageal anatomy and functionality will be monitored by performing manometry and barium esophagram at 12-months post-implant. This will allow for identification of any abnormal or atypical findings. Further, device migration will be assessed by confirming device position at the gastroesophageal junction (GEJ) by obtaining upright, bi-plane X-rays and device erosion will be assessed by performing endoscopy at the 12-month visit.

Efficacy will be assessed by evaluating the percentage of subjects reporting at the 12-month follow-up:

- Normalization of total distal acid exposure time or at least 50% reduction in total distal acid exposure time compared to baseline.
- >50% reduction in total GERD-HRQL score compared to baseline (off PPIs).
- >50% reduction in average daily PPI dosage compared to baseline.

2 Treatment Assignment

This is a prospective, multicenter, single-arm, observational study, where subjects serve as their own control.

3 Randomization and Blinding Procedures

This is an observational, single-arm study. No randomization will occur, and no blinding procedures will be needed.

4 Interval Windows

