Interval windows are not defined for the purpose of analysis in this study outside of the visit windows that are provided in the Study Schedule and Assessments in the final protocol. There will be no assigning of observations to time points outside of the visit to which they are recorded in the electronic Case Report Forms (eCRFs). Data collected in Unscheduled Visits forms will be listed as such. Observations collected outside of the 12-month protocol-specified visit window may be still be included in the analysis of primary effectiveness and safety endpoints since the device under study is an implant and longer term follow-up (i.e. beyond 12-months) is still considered informative towards evaluating the overall benefit-risk profile of the device in subjects with prior LSG surgery.

5 Levels of Significance

No formal statistical hypotheses are specified for this study. For continuous efficacy parameters, the p-value for a one sample, paired t-test to test if there is statistical evidence that the change from baseline is not equal to zero will be given. All estimation of endpoints will be performed using 95% confidence intervals.

6 Analysis Sets

All subjects who meet the eligibility criteria, provide informed consent, complete baseline assessments and undergo the LINX procedure will represent the study population for analysis. This set of subjects will be labeled as Full Analysis Set (FAS). This set of subjects will be identified by having answered “Yes” to the question “Was the LINX device implanted?” on the Implant Data eCRF.

7 Sample Size Justification

No formal sample size calculation has been performed for this study. The sample size planned for the study is up to 30 eligible subjects recruited from 12 clinical sites and no site will enroll more than 6 subjects without prior written approval provided by the Sponsor. No formal hypothesis has been tested in this study; thus, the sample size is not statistically sized, but rather is considered

sufficient for a descriptive summary of LINX performance for subjects who have had prior gastric surgery with LSG through confidence interval estimation and evaluation of safety and efficacy.

8 Analyses to be Conducted

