8.9 Handling of Missing Data

All summaries will be performed only on enrolled subjects and only observed data will be summarized. There will be no imputation of data for early terminated subjects or for missing data within the database.

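### Tables 6, 14 and 15 put no condition on later surgery, so a subject re-operated for reflux with the device in place could count as a LINX success

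*SAP*

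**What the plan says.** **Success.** The footnote to SAP Table 6 takes as successful the "number of subjects meeting the success criterion of pH normalization or at least 50% reduction in total distal acid exposure". Tables 14 and 15 use the same form for a reduction of at least half in GERD-HRQL score and in daily PPI use. The denominators are subjects with baseline and 12-month data. Table 14 adds completion per protocol requirements, which in the context of the questionnaire tables points to the off-medication conditions.

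**Population and data.** SAP section 6 puts every implanted subject in the Full Analysis Set, and no later event removes anyone. Under SAP 8.9, "only observed data will be summarized" and nothing is imputed. SAP section 4 allows results from after the 12-month window to be used.

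**Later surgery.** Protocol 11.9 deals with explant, after which study testing and questionnaires are no longer required. Exclusion 5 in Protocol 6.2 covers gastric revision only at entry: "Plans to surgically revise the gastric pouch (either known preoperatively or decided intraoperatively". Protocol 11.10 lists permitted reasons for withdrawal, including adverse event, the subject's best interest and an open category, but does not name re-operation. SAP 8.5 has no rule for a subject who has another operation and keeps the device.

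**Background.** Protocol 4.0 states: "Roux-en-Y Gastric bypass (RYGB) has been recommended as a conversion procedure for those who develop or continue to have reflux after LSG". It presents LINX as the less invasive alternative.

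**The concern.** In a single-arm study with each subject as their own control, a 12-month response is read as the effect of the device. If a second procedure for reflux comes between implant and the 12-month test, the result reflects both, and the need for that procedure suggests that the device alone did not control the reflux. The plan guards against other influences: pH and GERD-HRQL are measured off medication, and explant has its own path. A later reflux procedure with the device retained has none.

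SAP section 5 says "No formal statistical hypotheses are specified for this study", so the responder percentages are the main efficacy evidence for the stated objective, which is similarity to the premarket approval outcomes in support of a labeling change. They should mean what a reader will take them to mean.

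**Working it through.** **Nothing to reproduce.** SAP section 7 states "No formal sample size calculation has been performed for this study". The plan gives no expected response rate, performance goal or re-operation rate.

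**Inputs from the documents**
- Planned size (SAP 1.2): "Up to 30 subjects meeting the eligibility requirements will be implanted with LINX".
- Interval for the pH rate (SAP 8.5.1): "Two-sided 95% CI will also be constructed using exact Clopper-Pearson method".
- SAP 8.8 reports follow-up below expectation but gives no number.

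**Assumed inputs**
- n evaluable at 12 months: 30 (everyone) or 20.
- Observed success: 80%, so x = 24 of 30 or 16 of 20.
- k = 1 or 2 subjects re-operated for reflux with the device in place who meet the criterion.

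**Step 1: what the rule does.** Such a subject is in the Full Analysis Set, has baseline and 12-month data, and meets the criterion. The subject is therefore in both numerator and denominator, whatever surgery came between.

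**Step 2: formulas**
- Plan as written: x/n.
- Counted as non-responder: (x − k)/n. The difference from the plan is k/n.
- Withdrawn before the test: (x − k)/(n − k).
- Exact 95% limits for a count y of m: lower is the 0.025 quantile of Beta(y, m − y + 1); upper is the 0.975 quantile of Beta(y + 1, m − y).

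**Step 3: results**

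| n | k | As written | Non-responder | Withdrawn |
|---|---|---|---|---|
| 30 | 1 | 24/30 = 80.0% (61.4–92.3) | 23/30 = 76.7% (57.7–90.1) | 23/29 = 79.3% (60.3–92.0) |
| 30 | 2 | 24/30 = 80.0% (61.4–92.3) | 22/30 = 73.3% (54.1–87.7) | 22/28 = 78.6% (59.0–91.7) |
| 20 | 1 | 16/20 = 80.0% (56.3–94.3) | 15/20 = 75.0% (50.9–91.3) | 15/19 = 78.9% (54.4–93.9) |
| 20 | 2 | 16/20 = 80.0% (56.3–94.3) | 14/20 = 70.0% (45.7–88.1) | 14/18 = 77.8% (52.4–93.6) |

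The shift per subject, 1/30 = 3.3 points or 1/20 = 5.0 points, does not depend on the assumed 80%. The interval is 92.3 − 61.4 = 30.9 points wide at n = 30 and 94.3 − 56.3 = 38.0 points wide at n = 20, so one such subject moves the estimate by much less than its sampling uncertainty.

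**Step 4: could it occur?** If a share r of implanted subjects had such a procedure, the chance of at least one among 30 is 1 − (1 − r)^30. This is 0 at r = 0, 45% at r = 2% and 79% at r = 5%. These values of r are assumptions, and the chance is of the procedure occurring, not of its being scored a success.

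**The case against.** **The plan is silent; it does not say that these subjects count.** True. Several things must coincide: a reflux procedure before the 12-month test, the device kept, no withdrawal, the test done and the criterion met. Protocol 11.10 would allow withdrawal, and a re-operated subject who misses the criterion is already a failure. But the definitions, applied literally, give one answer when all the conditions hold. A withdrawn subject leaves the denominator and is still not counted as a failure.

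**The protocol does not describe surgery after a failed LINX.** Also true. Its RYGB text concerns reflux after the sleeve, and the later device surgery it provides for is explant. A reader might infer that conversion with the device in place is expected; the documents do not say so. They show only that a further operation for reflux is a known option in this population.

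**Using the observed value whatever happens later is a recognised choice.** It is, and the plan may make it, but it should then say so and show how many subjects it affects.

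**The bias always favours the device.** A reader might infer this, but it does not hold for every later operation. These subjects had their sleeve for obesity, and a revision for weight or sleeve reasons need not mean that reflux control failed. Scoring every revision as a failure could bias against the device. The non-responder rule is justified only for procedures done for reflux.

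**The listings would show it.** In part. SAP 8.1 lists all eCRF data, and Protocol 5.1 includes hospital readmissions in the safety assessment. But Protocol 11.9 limits reportable events to those strongly related to the device or implant procedure, so surgery for persisting reflux may not appear as an adverse event. Medical history is marked at 12 months in the synopsis schedule and Protocol Table 1 but is missing from the 12-month list in Protocol Table 3.

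**Conclusion.** The gap is real and of low priority. As the tables stand, a subject re-operated for reflux with the device in place, tested at 12 months and meeting the criterion would be scored as a LINX success on each endpoint met. Each such subject would raise a rate by 3.3 points at n = 30, or 5.0 points at an assumed n = 20, compared with counting that subject as a non-responder.

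The documents do not support the stronger conclusion that the reported rates will be inflated. They give no frequency for the event and no indication of how often the device would be kept, so the number may be zero. The falls from 80% to 70% or 73.3% come from assumed counts. With no hypothesis test or performance goal, no pass-or-fail result can change.

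One caveat: the SAP table shells between Table 21 and Table 29 were not in the text available, so a rule placed there cannot be excluded. The surviving note from that part concerns explants.

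**What to change.** Scoring and reporting only:

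1. In SAP 8.5 and the footnotes of Tables 6, 14 and 15, state that a subject with a further surgical or endoscopic procedure done for reflux between implant and the 12-month assessment is a non-responder in the three responder endpoints. Procedures done at the implant operation itself are not affected.
2. Report gastric revisions done for other reasons separately, with a sensitivity analysis that counts them both ways.
3. Give the number of subjects affected, and the observed-value rate as a sensitivity analysis.
4. Record the type, date and reason of any such procedure at follow-up, and reconcile the synopsis schedule and Protocol Table 1 with Protocol Table 3 on medical history at 12 months.

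The cost is a sentence in SAP 8.5, three footnotes and a small addition to data capture. The reported rate would be slightly lower if any such subject exists. If none does, the rates stay the same and the report can say so.
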